5.13.3. Time to Response

Time to response (TTR) is the time from the date of first study treatment until the first evidence of a confirmed CR or PR. If a patient did not experience a confirmed CR or PR, the TTR will be censored at the treatment starting date.

Time to response will be estimated using Kaplan-Meier (KM) method (Kaplan and Meier 1958) and summary statistics including median and 95% CI will be presented.

5.13.5. Duration of Response

The duration of response (DoR) time is defined only for responders (patients with a confirmed CR or PR). It is measured from the date of first evidence of CR or PR to the date of the first observed radiographically documented PD, or the date of death due to any cause, whichever is earlier. For clarity, the start date should be determined by the initial assessment of CR or PR, not the date of confirmation of CR or PR. It is calculated as date of progression or death – date of first response evaluation of CR or PR + 1.

Duration of response will be censored according to the same rules as PFS, with the addition of the following rule: if a patient begins postdiscontinuation therapy, DoR will be censored on the day of the last response evaluation prior to the initiation of postdiscontinuation therapy.

Duration of response will be estimated using KM method and summary statistics including median and 95% CI will be presented.

5.13.6. Immuno-Related Efficacy Analysis Variables

Study JZDA will use RECIST 1.1 with confirmatory scan for disease progression. Detailed application of RECIST 1.1 with confirmatory scan for PD can be found in Protocol J1C-MC-JZDA, Section 9.1.1.2.

Immune-related objective response rate (irORR) is defined as the proportion of treated patients achieving a best overall response of CR or PR per RECIST 1.1 with confirmatory scan for PD. Particularly, the best overall response by RECIST 1.1 with confirmatory scan for PD closely related to confirmed response by RECIST. Immune-related objective response rate further captures responses after unconfirmed PD and it does not require confirmation. For example:

- If the best response by RECIST 1.1 is CR, then the best response by RECIST 1.1 with confirmatory scan for PD is CR.
- If the best response by RECIST 1.1 is PR, SD, or PD, the best response by RECIST 1.1 with confirmatory scan for PD is the best response over the initial assessment (prior to PD by RECIST) and the confirmation stage.

Overall, the best response by RECIST 1.1 with confirmatory scan for PD should be the same or better than the best response by RECIST criteria. In addition, patients who do not have any postbaseline tumor response assessments for any reason are considered non-evaluable and will be included in the denominator when calculating the response rate.

Immune-related disease control rate (irDCR) is defined as the number of patients with immune-related stable disease (irSD), immune-related complete response (irCR), or immune-

related partial response (irPR) divided by the number of enrolled patients who have received any quantity of study treatment.

Immune-related time to response (irTTR) is the time from the date of first study treatment until the first documented irCR or irPR.

Immune-related PFS (irPFS): The date from the treatment start date to the time of PD assessed by RECIST 1.1 with confirmatory scan for PD.

- If the initial PD is confirmed, then the date of immune-related partial disease (irPD) is the initial PD date by RECIST 1.1.
- If the initial PD is unconfirmed, then the date of irPD is the date of second PD.

Immune-related duration of response (irDOR): The duration of response is defined from the date of first documented irCR or irPR (responder) to the date of irPD or the date of death due to any cause, whichever is earlier.

In addition, the best response after initial PD may be listed.

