Sample collection											See Appendix 4 for pharmacodynamics, pharmacokinetics, immunogenicity, pharmacogenetics, tumor tissue, and other biomarkers.
Administer LY3415244			X	X	X	X	X	X	X	X	LY3415244 will be administered as an IV infusion over approximately 60 minutes, depending on dose level (doses ≤ 70 mg may require bolus IV injection administration over 5 to 10 minutes). In Cycles 1 to 3, the LY3415244 infusion will be followed by a 4-hour observation period.

Baseline and On-Study Treatment Schedule of Activities

Abbreviations: AE = adverse event; C1D1 = Cycle 1 Day 1; CTCAE = Common Terminology Criteria for Adverse Events; ECG = electrocardiogram; ECHO = echocardiogram; ECOG PS = Eastern Cooperative Oncology Group performance status; ESR = erythrocyte sedimentation rate; HCC = hepatocellular carcinoma; HIV = human immunodeficiency virus; ICF = informed consent form; IV = intravenous; MUGA = multiple-gated acquisition; Q = every; RECIST 1.1 = Response Criteria in Solid Tumors Version 1.1; W = weeks.

Table JZDA.2.2. Poststudy Treatment Follow-Up Schedule of Activities

Procedure	Follow-Up Visit				Instructions	
	Short-Term ^a			Long-Term (Q90D) ^b		
	30-Day Visit	60-Day 801	90-Day 802			
Pregnancy test	X		X		Perform pregnancy test for women of childbearing potential	
ECG					See Appendix 4 for ECG collection instructions	
Physical examination	X				Including weight and vital signs (temperature, blood pressure, pulse rate, and respiration rate)	
Concomitant medication	X					
AE collection	X	X	X	X	CTCAE Version 4.0. During the 30-, 60-, and 90-day follow-up visits, collect all AEs/SAEs. Thereafter, collect only SAEs related to study treatment or protocol procedures	
ECOG performance status	X					
Tumor imaging/assessment	X				For patients who discontinue study treatment without objectively measured PD, continue to perform tumor assessment and imaging every 6 to 12 weeks according to the standard of care	
Collection of survival information	X	X	X	X	In-person office visits are not required; the site may confirm survival by contacting the patient directly via telephone or other means of communication (for example, email)	
Collection of poststudy-treatment anticancer therapy information	X	X	X	X	Discontinuation from study treatment must occur prior to introduction of the new agent	
Laboratory tests	X				Perform hematology, coagulation, clinical chemistries, and thyroid function tests	

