8.1. Discontinuation from Study Treatment

Patients will be discontinued from study treatment in the following circumstances:

- the patient is enrolled in any other clinical study involving an investigational product or any other type of medical research judged not to be scientifically or medically compatible with this study.
- the patient becomes pregnant during the study
- the patient is significantly noncompliant with study procedures and/or treatment as described in Section 7.6
- The patient experiences a DLT (see Section 7.2.2.2) during Cycle 1, a DLT-equivalent toxicity (see Section 7.2.2.2.2), or other unacceptable toxicity
- the patient requires a dose delay of >28 days, except as described in Section 7.4
- the patient, for any reason, requires treatment with another therapeutic agent that has been demonstrated to be effective for treatment of the study indication.
Discontinuation from study treatment will occur prior to introduction of the new agent
- the investigator decides that the patient should be discontinued from study treatment
- the patient requests to be discontinued from study treatment
- the patient has received the maximum duration of 12 months of study treatment (longer duration may be considered for a patient receiving clinical benefit, in consultation with the Lilly CRP/CRS). If tumor imaging shows initial disease progression, at the discretion of treating physician, patients may remain on study treatment with repeat imaging 4 to 6 weeks later to assess tumor response or confirm progression per RECIST 1.1 with confirmatory scan on disease progression

Patients who are discontinued from study treatment will have follow-up procedures performed as shown in the Schedule of Activities (Section 2).

Discontinuation of study treatment may be considered for patients who meet all of the following criteria:

- have a confirmed CR, **and**
- have received study treatment for at least 24 weeks, **and**
- have received at least 2 cycles of study treatment beyond the date when the initial CR was declared.

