9.1.1. RECIST 1.1 with Confirmatory Scan for Disease Progression

9.1.1.1. Rationale for RECIST 1.1 with Confirmatory Scan for Disease Progression

Response to immunotherapy may differ from responses typically observed with cytotoxic chemotherapy, including the following (Wolchok et al. 2009; Nishino et al. 2013):

- Response to immunotherapy may be delayed.
- Response to immunotherapy may occur after PD by conventional criteria.
- The appearance of new lesions may not represent PD with immunotherapy.
- Stable disease while on immunotherapy may be durable and represent clinical benefit.

Therefore, to adequately characterize additional patterns of response and progression specific to patients treated with immunotherapy, which cannot be captured by conventional criteria such as RECIST 1.1, alternative measures of tumor assessment have been developed: (i) RECIST 1.1 with confirmatory scan for disease progression and (ii) immune-related response criteria (irRC, Wolchok et al. 2009). For both measures (i) and (ii), clinically stable patients may continue treatment until disease progression (per standard RECIST 1.1) is confirmed. As the irRC are still being developed and validated for various tumor types, Study JZDA will use RECIST 1.1 with confirmatory scan for disease progression, which may discourage the early discontinuation of study treatment and provide a more complete evaluation of its efficacy than would be seen with conventional response criteria.

Table JZDA.9.1. Summary of Response Assessment by RECIST, RECIST with Confirmatory Scan for PD, and irRC

Definition	Used in Study JZDA		Not Used in Study JZDA
	RECIST v1.1	RECIST 1.1 with Confirmatory Scan for PD	irRC (Wolchock et al. 2009), irRECIST (Nishino et al. 2013) iRECIST (Seymour et al. 2017)
New lesion	The presence of new lesion defines progression	The presence of new lesion defines progression	The presence of new lesion does not define progression. The measurements of the new lesion(s) are included in the sum of the measurements.
Confirmation of PD	Not required	PD, in the absence of clinically significant deterioration, requires confirmation with repeat imaging after 4-6 weeks. After initial PD following RECIST v1.1, shift to “RECIST 1.1 with confirmatory scan for PD”.	Required

Abbreviations: irRC = immune-related response criteria; irRECIST = immune-related Response Evaluation Criteria in Solid Tumors PD = progressive disease; RECIST = Response Evaluation Criteria in Solid Tumors.

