9.1.1.2. Application of RECIST 1.1 with Confirmatory Scan for Disease Progression

For Study JZDA, based on the unique response to immunotherapy and guidelines from regulatory agencies (for example, the EMA guideline on the evaluation of anticancer medicinal products in man for immune-modulating anticancer compounds [EMA 2013]), the following will be applied, in addition to standard RECIST 1.1 criteria:

- If radiologic imaging verifies initial PD, tumor assessment should be repeated 4 to 6 weeks later in order to confirm PD in the absence of clinically significant deterioration. Study treatment will continue between the initial assessment of progression and confirmation for progression (see Section 9.1.1.3).

“Clinically significant deterioration” is considered to be rapid tumor progression that necessitates treatment with anticancer therapy other than study treatment, or symptomatic progression that requires urgent medical intervention (for example, rapid disease progression or threat to vital organs or critical anatomical sites, such as central nervous system metastasis, respiratory failure due to tumor compression, or spinal cord compression).

- In the case of clinically significant deterioration, the patient will be discontinued from study treatment (Section 8.1).
- Patients who continue to receive clinical benefit and who do not have clinically significant deterioration despite evidence of objective PD by the confirmatory scan may continue study treatment at the discretion of the investigator, in consultation with the Lilly CRP/CRS.

In determining whether or not progression can be confirmed, the site study team should consider all target lesions, nontarget lesions, and new lesions.

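### SAP 5.13.6 gives no irPD date for a first progression without a repeat scan; read literally, such patients have no irPFS event, and irDOR is left only with death

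*SAP*

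**What the plan says.** SAP 5.13.6 has two branches for the date of irPD. (The SAP spells PD out as partial disease; progressive disease is evidently meant.)

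- Confirmed: "If the initial PD is confirmed, then the date of immune-related partial disease (irPD) is the initial PD date by RECIST 1.1".
- Unconfirmed: "If the initial PD is unconfirmed, then the date of irPD is the date of second PD".

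The irPFS definition reads "The date from the treatment start date to the time of PD assessed by RECIST 1.1 with confirmatory scan for PD". It does not mention death, and 5.13.6 gives no censoring rule. The irDOR definition does include death: it runs "to the date of irPD or the date of death due to any cause, whichever is earlier".

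On when a confirmatory scan is needed and obtained, the protocol says:

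- Table JZDA.9.1: "PD, in the absence of clinically significant deterioration, requires confirmation with repeat imaging after 4-6 weeks".
- Section 9.1.1.2: "In the case of clinically significant deterioration, the patient will be discontinued from study treatment". Without deterioration, a repeat assessment is requested 4 to 6 weeks later.
- Section 8.1: after initial progression, "at the discretion of treating physician, patients may remain on study treatment with repeat imaging 4 to 6 weeks later".
- Section 9.1: on-treatment imaging runs until the first of several stops, among them progression confirmed on a second examination and the start of new anticancer treatment. After treatment, assessments may continue for patients withdrawn for reasons other than progression.
- Table JZDA.2.2: the imaging row has an X at the 30-day visit, with the instruction "For patients who discontinue study treatment without objectively measured PD, continue to perform tumor assessment and imaging every 6 to 12 weeks".

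Protocol 10.3.2 and SAP 5.13 call for response, PFS and DoR under both RECIST 1.1 and RECIST 1.1 with confirmatory scan.

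**The concern.** A first PD can end in three ways: a repeat scan shows PD, a repeat scan does not show PD, or there is no repeat scan. The SAP provides for two. The third is foreseeable. Patients with clinically significant deterioration come off treatment, others may stop because continuation is discretionary, and a new anticancer therapy ends imaging.

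If these patients go to the second-PD branch, their documented progression drops out of irPFS and irDOR. The loss is informative, because patients who deteriorate at first PD are among those least likely to be scanned again. The two analysis sets will be read side by side, so any excess of irPFS over PFS could be taken as benefit beyond first progression when part of it is only missing scans.

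**Working it through.** The documents give no figure for irPFS or irDOR to reproduce. The check is a reading of the rules, followed by an illustration of size.

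**Step 1. Apply the rules to each kind of first PD.**

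| After first PD | Does the protocol direct a repeat scan? | irPD date, SAP 5.13.6 read literally |
|---|---|---|
| Continues treatment, repeat scan shows PD | Yes (9.1.1.2) | Initial PD |
| Continues treatment, repeat scan does not show PD | Yes (9.1.1.2) | Second PD |
| Clinically significant deterioration, taken off treatment | Not required (Table JZDA.9.1) | Second PD, generally not collected |
| No deterioration, but stops treatment | Requested by 9.1.1.2; continued imaging in 9.1 and Table JZDA.2.2 is directed to patients without PD; 30-day X present | Second PD, if any scan is done |
| Starts new anticancer therapy before a repeat scan | Imaging ends (9.1) | Second PD, not collected |

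Where no second PD is recorded, irPFS has no event, since death is not in its definition. irDOR can end only at death. Row 3 also conflicts with Table JZDA.9.1: a PD that needs no confirmation is left waiting for a second one.

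**Step 2. Size under simple censoring.** Assumptions, none from the documents: exponential PFS with a true median of 2 months; a fraction f of first PDs without a repeat scan, chosen at random; censoring at the first PD scan. SAP 5.13.6 states no censoring date. The first PD scan is what results from borrowing Table JZDA.5.2, whose note counts a PD scan as adequate.

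Hazard h = ln 2 / 2. The hazard of counted events is (1 − f)h, so the estimated median is ln 2 / [(1 − f)h] = 2 / (1 − f).

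- f = 30%: 2 / 0.7 = 2.9 months
- f = 50%: 2 / 0.5 = 4.0 months
- f = 70%: 2 / 0.3 = 6.7 months

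**Step 3. The same effect on the trial's scan schedule.** From the documents: scans every 8 weeks in year 1 (Table JZDA.2.1), 20 patients per expansion cohort (Protocol 5.2), and 24 weeks as a landmark for PFS (SAP 5.13.4). Assumed: true median 12 weeks, no deaths, a random share q without a repeat scan.

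The chance of progression per scan interval is 1 − 2^(−8/12) = 0.370. Estimated 24-week irPFS, three scans, is [1 − (1 − q) × 0.370]³. Expected events by week 48 are 20 × (1 − 2^(−48/12)) × (1 − q) = 18.75 × (1 − q).

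| q | 24-week irPFS | Events per 20 |
|---|---|---|
| 0 | 25% | 18.75 |
| 25% | 0.7225³ = 38% | 14.1 |
| 50% | 0.815³ = 54% | 9.4 |
| 75% | 0.9075³ = 75% | 4.7 |

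**Step 4. Would adding death alone repair it?** Keep the 2-month median and assume a median survival of 4 months after PD, with no deaths before PD. Let x = 2^(−t/4). The estimated curve is (1 − f)x² + f(2x − x²). Setting it to 0.5 gives x = 0.596, 0.500 and 0.404, so t = 3.0, 4.0 and 5.2 months at f = 30%, 50% and 70%. The event is then the death date rather than the PD date, and the upward bias remains.

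**The case against.** The strongest reply is that the SAP never says a missing scan counts as unconfirmed. The term is undefined, and it can naturally mean a repeat scan that failed to show PD. SAP 5.13.6 also refers to Protocol 9.1.1.2 for detailed application, where confirmation applies only without deterioration, so a PD with deterioration might keep its initial date. This stands as far as it goes: the plan is ambiguous, and a reader who infers an explicit misclassification goes beyond the text. But 9.1.1.2 assigns no irPD date when there is no scan, and it does not cover patients without deterioration who stop, decline the scan or die first. On the favourable reading those patients have no rule, and a date would have to be chosen after the data are seen.

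A reader might also infer that the schedule never collects a second scan. The documents do not support that. Section 9.1.1.2 requests a scan at 4 to 6 weeks without making it depend on continued dosing, and Table JZDA.2.2 has the 30-day X. Nor does Section 9.1.1.3 bar scanning: its criteria on performance status and addendum consent govern continued dosing. What remains is that a second scan is not reliably collected after treatment stops at first PD.

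Finally, RECIST 1.1 is the primary criterion, ordinary PFS has its own censoring table, and no hypothesis test is planned (SAP 5.6). That is correct and limits the consequence to descriptive estimates.

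**Conclusion.** The point holds as a gap in the rule with a predictable direction of bias. SAP 5.13.6 neither defines 'unconfirmed' nor dates a first PD without a repeat scan. The literal reading removes the irPFS event for such patients and leaves irDOR only with death, so both estimates would be too favourable relative to RECIST 1.1 PFS and DoR.

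The size cannot be estimated from the documents. The medians of 2.9, 4.0 and 6.7 months against a true 2 months, and the 24-week figures, rest wholly on assumed inputs. They also treat the missing scans as random, so they do not model the informative loss described above. No size is offered for irDOR. No error rate and no primary endpoint is affected. The change should be made before analysis because the comparison of irPFS with PFS is open to misreading and the repair is small.

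**What to change.** In SAP 5.13.6:

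1. Define 'unconfirmed' as an adequate repeat scan that does not show PD; irPD is then the next documented PD.
2. If no adequate repeat scan was obtained for any reason (deterioration, stopping treatment, new therapy, refusal, death), set irPD to the initial RECIST 1.1 PD date. This agrees with Table JZDA.9.1.
3. Add death from any cause as an irPFS event, and apply the censoring rules of Table JZDA.5.2 to irPFS and irDOR. Say that therapy started after an initial PD dated under rule 2 does not turn that PD into a censored observation.
4. Report the number of first PDs without a repeat scan, with a sensitivity analysis that censors them.

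Separately, Protocol 9.1, 9.1.1.2 and Table JZDA.2.2 should be reconciled on imaging for patients who stop at first PD.

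Cost: a few SAP sentences, one count and one sensitivity analysis, with no new data. irPFS and irDOR become slightly less favourable, and a rare pseudoprogression without a repeat scan will count as PD; the sensitivity analysis shows how much that matters.

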5.13.7. Overall Survival

Overall survival is defined as the time from first study treatment until death due to any cause. If the patient is not known to have died at the data inclusion cutoff date for the analysis (or is lost to follow-up), OS data will be censored on the last date the patient is known to be alive.

Overall survival will be estimated using KM method. Median OS along with 95% CI as well as OS rates (and 95% CI) at 1 and 2 years will be presented.

5.14. Subgroup Analyses

Subgroup analyses of efficacy endpoints may be performed for each of the potential prognostic subgroup variables listed below.

- sex (male; female)
- age (<65 years; ≥65 years; <70 years; ≥70 years)
- baseline Eastern Cooperative Oncology Group (ECOG) PS (0; 1)
- ethnicity (White; East Asian; others)
- smoking status (never; current; former)
- prior lines of therapy (such as first line, second line, third line and beyond)

Other subgroups may be added as deemed necessary.

5.15. Immunogenicity Analysis

Immunogenicity (anti- LY3415244 antibody) incidence will be tabulated, and correlation to drug level, activity, and safety will be assessed, as appropriate, respectively. The measures that will be analyzed include baseline presence and level of anti-drug antibodies (ADA), treatment-

emergent ADA, levels of neutralizing ADA, and incidence and levels of ADA related to infusion-related reactions.

5.16. Pharmacokinetic/Pharmacodynamic Analyses

Pharmacokinetic parameter estimates for LY3415244 therapy will be calculated by population PK analysis methods using nonlinear mixed effects modeling. The version of any software used for the analysis will be documented, and the program will meet the Lilly requirements of software validation. It is possible that other validated, equivalent PK software programs may be used if appropriate, warranted, and approved by Lilly global PK/pharmacodynamic management. In addition, selected PK parameters (based on actual sampling times), including maximum observed drug concentration (C_{max}), time of C_{max} , and area under the concentration versus time curve (AUC) may be calculated by noncompartmental analysis methods and/or model simulations. As an exploratory analysis, PK parameter estimates for minimum observed drug concentration during a dosing interval (C_{min}) at steady state following repeated dose may be evaluated.

Pharmacokinetic/pharmacodynamic analyses will be conducted to explore exposure-response relationships between LY3415244 concentrations in systemic circulation and various pharmacodynamic measures, such as selected safety outcomes, receptor occupancy, and biomarkers.

